7. STUDY TREATMENT

7.1. Investigational Product and Other Study Treatment

The term 'study treatment' is used throughout the protocol to describe any combination of products received by the subject as per the protocol design. Study treatment may therefore refer to the individual study treatments or the combination of those study treatments.

Albuterol/salbutamol will be given to all subjects to use throughout the study to treat acute asthma symptoms as needed per product label. Only study-supplied albuterol/salbutamol should be used for rescue during the study. Rescue usage will be recorded once daily in the subject's paper diary. **Do not record albuterol/salbutamol use in the eCRF.**

Albuterol/salbutamol inhalation aerosol will be supplied as detailed in the SRM.

	Study Treatment			
Product name:	Fluticasone Furoate/ Vilanterol 100/25 mcg	Fluticasone Propionate 250 mcg	Placebo ELLIPTA	Placebo DISKUS/ ACCUHALER
Formulation:	First strip: FF 100 mcg blended with lactose Second strip: VI 25 mcg blended with lactose and magnesium stearate	FP 250 mcg blended with lactose.	First strip: lactose Second strip: blend of lactose and magnesium stearate	Lactose
Dosage form:	ELLIPTA – 30 doses per device	DISKUS/ ACCUHALER – 60 doses per device	ELLIPTA – 30 doses per device	DISKUS/ ACCUHALER – 60 doses per device
Unit dose strength(s)/Dosage level(s):	100/25 mcg per actuation	250 mcg per actuation	NA	NA
Route of Administration	Inhaled	Inhaled	Inhaled	Inhaled
Dosing instructions:	Once daily in the evening	Twice daily; once in the morning and once in the evening	Once daily in the evening	Twice daily; once in the morning and once in the evening

FF= fluticasone furoate; VI = vilanterol; FP = fluticasone propionate; mcg = micrograms; NA = not applicable

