8.3.3.2. Visit 2 (Randomization)

Treatment period 1 baseline FEV₁: Visit 2 begins between 5 PM and 11 PM and should begin at approximately the same time as Visit 1 (± 1 hour). Spirometry will be performed at Visit 2 at approximately the same time as at Visit 1 (± 1 hour). The FEV₁ should be measured approximately 12 hours (± 1 hour) after dosing with run-in medication (FP 250 mcg). At least two valid and two repeatable spirometry efforts should be obtained before the first exercise challenge.

From this spirometry testing, the target FEV₁ values #2 and #3 (Section 8.3.1.1) should be determined based on the pre-exercise FEV₁.

Eligibility Exercise Challenge: After the pre-exercise baseline FEV₁ has been determined, an exercise challenge will be performed according to the method described in the SRM.

Post-exercise Serial Spirometry: Following the eligibility exercise challenge, serial spirometry (FEV₁) will be performed at 5, 10, 15, 30, 45 and 60 minutes post-exercise.

To qualify for randomization, subjects must demonstrate a decrease in FEV₁ of $\geq 20\%$ when compared to the FEV₁ obtained immediately pre-exercise for at least one of the post-exercise spirometry efforts obtained within 30 minutes post-challenge. Subjects who achieve a decrease in FEV₁ of 15% to $< 20\%$ may continue taking their daily run-in medication and repeat the eligibility exercise challenge **once** within a week. In the event where a repeat visit is required for the exercise challenge, spirometry and vital signs measurements will be performed pre- and post- exercise challenge as detailed in [Table 3](#). In addition, ACQ-5 and a review of concomitant medication and adverse events will be performed at the repeat visit.

Dosing: Eligible subjects will administer their evening dose of double-blinded study medication following the eligibility exercise challenge/serial spirometry. Evening dosing should occur between 5 PM and 11PM.

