8.3.3.4. Visit 4 and Visit 7 (Blinded Treatment Exercise Challenges)

Visit 4 and Visit 7 begin between 5 PM and 11 PM and are conducted over approximately 24 hours. Subjects will be required to attend three clinic visits during each 24-hour period for Visit 4 and Visit 7. The evening visit should begin at approximately the same time as Visit 1 (± 1 hour).

Dosing: At the beginning of Visit 4 and Visit 7, subjects will administer their evening doses of double-blinded study medication in the clinic and the time of dosing will be recorded. In addition to administering the evening dose, vital signs will be measured and a review of concomitant medication and AEs performed.

Subjects will return to the clinic 12 (± 1) hours and 23 (± 1) hours after evening dosing for exercise challenge testing.

Pre-exercise FEV₁: At least two valid spirometry efforts with full FEV₁ and FVC maneuvers should be obtained just prior to each exercise challenge.

From this spirometry testing, the target FEV₁ values #2 and #3 (Section 8.3.1.1) should be determined based on the pre-exercise FEV₁.

Exercise challenge testing: Exercise challenge testing will occur at 12 (± 1) hours and 23 (± 1) hours after administering the evening dose. (The 12-hour exercise challenge and spirometry measurements should occur prior to dosing of the study medication).

Post-exercise Serial Spirometry: Following the eligibility exercise challenge at each visit, serial spirometry (FEV₁) will be performed at 5, 10, 15, 30, 45 and 60 minutes post-exercise.

Washout Medication Dosing: At the end of Visit 4, the washout medication should be dispensed and first evening dose administered following completion of the 23-hour post evening dose exercise challenge/serial spirometry, and prior to the subject's leaving the clinic.

8.3.3.5. Visit 5

Treatment period 2 baseline FEV₁: Spirometry will be performed at Visit 5 at approximately the same time as at Visit 1 (± 1 hour). The FEV₁ should be measured approximately 12 hours (± 1 hour) after dosing with the washout medication. At least two valid spirometry efforts should be obtained.

Dosing: Subjects will administer their evening doses of double-blinded study medication following the spirometry.

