10.1. Appendix 1: Definitions for Per Protocol Population

10.1.1. Protocol Deviations Impacting the Per Protocol Population

A protocol deviation which could affect all treatment periods will be considered a full deviation and will result in exclusion from the Per Protocol population. A protocol deviation which would only affect a specific treatment period will be considered a partial deviation and the data from the treatment period affected by the deviation will be excluded. If a subject has partial deviations in both treatment periods then the subject will be excluded from the Per Protocol population, however if a subject only has partial deviations in 1 treatment period, they will be considered part of the PP population but their data from the treatment period affected by the deviations will be excluded.

Reasons for protocol deviations that will impact the Per Protocol population include the following:

Number	Exclusion Description	Full or Partial?
1	Failure of inclusion criteria 3, 4, 5, 6 or 9; exclusion criteria 1, 3, 4, 7, 8, 9, 12, 13 or 15; randomization inclusion criteria 1 or 2 or randomization exclusion criteria 2, 4 or 5 as described in Section 6 of the protocol [GlaxoSmithKline Document Number 2015N231308_03].	Full
2	Remaining in the study after meeting the following withdrawal criteria described in Section 6 of the protocol [GlaxoSmithKline Document Number 2015N231308_03]: 
 Severe asthma exacerbation 	Full if during 1 st treatment period. Otherwise partial.
3	Taking of prohibited medication as described in Section 7.10.2 of the protocol [GlaxoSmithKline Document Number 2015N231308_03], where that medication could conceivably have an effect on a subject's efficacy.	Full if it affects both periods. Otherwise partial.
4	Overall treatment compliance for either DISKUS or ELLIPTA of < 80% or > 120%. (The protocol required subjects to take their study medication each day. For reporting and analysis purposes, treatment compliance of 80% and 120% are defined here as lower and upper limits for subjects to remain in the Per Protocol population.) Only treatment periods affected will be excluded.	Partial
5	Taking the wrong treatment at any time during the study. Only treatment periods affected will be excluded.	Partial

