Exposure will be calculated for each type of inhaler (DISKUS and ELLIPTA) separately. The number of days on study drug for each subject and treatment period will be calculated as (date treatment stopped – date treatment started) + 1. The treatment start and stop dates used will be the earliest and latest of all dates recorded for the subject and treatment period in question.

Treatment Compliance

Overall percentage treatment compliance for every subject will be calculated for each type of inhaler (DISKUS and ELLIPTA) and for each treatment period separately.

Compliance for the DISKUS and ELLIPTA will be based on the total number of inhalations taken from each type of inhaler and the expected number of inhalations to be taken. The expected number of inhalations will be derived as the expected number of inhalations per day (from each inhaler) multiplied by the number of days on study drug for the treatment period in question based on the subjects treatment start and stop date for that type of inhaler.

The total number of inhalations taken will be based on the dose counter for each type of inhaler. If there is no dose counter information at all for a given treatment period then the compliance will be missing, however, as long as the information from one dose counter is present, the compliance for that treatment period will be calculated. If a dose counter start count is missing then it will be assumed to be 30 for the ELLIPTA and 60 for the DISKUS.

In each calculation, all inhalers dispensed will be used, provided the dose counter stop counts are non-missing. The following formula will be used:

$$\text{Overall_Compliance} = \left(\frac{\text{Total_Number_of_Inhalations_Taken}}{\text{Expected_Inhalations} \times (\text{Stop_Date} - \text{Start_Date} + 1)} \right) \times 100$$

Where *Total_Number_of_Inhalations_Taken* is the total number of doses taken from all DISKUS or ELLIPTA inhalers in the treatment period in question, *Expected_Inhalations* is equal to 2 for the DISKUS and 1 for the ELLIPTA and *Start_Date* and *Stop_Date* are the earliest treatment start date and the latest treatment stop date recorded for all of the inhalers used in the calculation.

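### The SAP's DISKUS compliance denominator counts evening-only or morning-only days as two doses, so full adherence scores 93.75% or 96.7% and the 80%/120% Per Protocol limits shift for borderline periods

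*SAP*

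**What the plan says.** **Score.** SAP 10.6.2 (Treatment Compliance) takes the numerator from the inhaler: "The total number of inhalations taken will be based on the dose counter for each type of inhaler". The denominator is the daily expectation, which "is equal to 2 for the DISKUS and 1 for the ELLIPTA", times an inclusive count of calendar days. The same section counts days on study drug as "date treatment stopped – date treatment started) + 1". Compliance is calculated per inhaler type and per treatment period.

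**Use.** SAP 10.1.1, item 4, makes this a Per Protocol criterion: "Overall treatment compliance for either DISKUS or ELLIPTA of < 80% or > 120" (per cent) is a partial deviation, and only the affected period is dropped. SAP section 4 restricts the Per Protocol population to the confirmatory analysis of the primary endpoint.

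**Schedule.** Protocol 7.1 gives the DISKUS "Twice daily; once in the morning and once in the evening".
- Period 1 starts in the evening of Visit 2 (Protocol 8.3.3.2): "Eligible subjects will administer their evening dose of double-blinded study medication following the eligibility exercise challenge/serial spirometry".
- Period 2 starts in the evening of Visit 5 (Protocol 8.3.3.5): "Subjects will administer their evening doses of double-blinded study medication following the spirometry".
- At Visit 4/7 (Protocol 8.3.3.4) the evening dose is taken in the clinic and the subject returns 12 hours later. There, "The 12-hour exercise challenge and spirometry measurements should occur prior to dosing of the study medication". In Period 1, the next evening dose is washout medication.

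Protocol 8.3.1 separately tells subjects not to take study drug before attending on visit days.

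**The concern.** The numerator counts single doses and the denominator counts whole days. For a once-daily evening inhaler the two agree. For a twice-daily inhaler started in the evening they do not: the first calendar day can supply only one study dose but is charged as two. If the last dose is a morning dose, the last day is charged the same way. A subject who misses nothing then scores below 100%, and a limit set on that score is not the same percentage of the doses the schedule offers.

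Two things are at stake: whether the DISKUS compliance table reads correctly, and which periods near the limits enter the Per Protocol analysis.

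**Working it through.** The SAP gives no worked compliance value, so there is no published figure to reproduce. The ELLIPTA serves as a check on the formula: evening doses on Day 0 to Day 14 give 15 taken, with 1 × (14 − 0 + 1) = 15 expected, so 15/15 = 100%.

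**Assumptions.** The Visit 4/7 evening is Day 14 of the period, counting the Visit 2/5 evening as Day 0. The recorded stop date is the date of the last DISKUS dose.

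**Score at full adherence** = scheduled doses ÷ [2 × (stop − start + 1)].
- Last dose on the Visit 4/7 evening (Day 14): 1 + 14 × 2 = 29 doses; expected 2 × 15 = 30; 29/30 = 96.7%.
- Last dose the next morning (Day 15): 1 + 14 × 2 + 1 = 30 doses; expected 2 × 16 = 32; 30/32 = 93.75%.

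For a Visit 4 on Day 12 to Day 16 (the ±2-day window), these become 25/26 to 33/34 (96.2% to 97.1%) and 26/28 to 34/36 (92.9% to 94.4%).

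**Effective limit** = stated limit × expected ÷ scheduled.
- 29-dose schedule: 0.80 × 30/29 = 82.8%; 1.20 × 30/29 = 124.1%.
- 30-dose schedule: 0.80 × 32/30 = 85.3%; 1.20 × 32/30 = 128%.

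**In whole doses:**

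| Schedule | Inside 80–120% of scheduled doses | Accepted by the SAP formula | Misclassified |
|---|---|---|---|
| 30 doses | 24 to 36 | 26 to 38 (0.80 × 32 = 25.6; 1.20 × 32 = 38.4) | 24, 25 excluded; 37, 38 kept |
| 29 doses | 24 to 34 (0.80 × 29 = 23.2; 1.20 × 29 = 34.8) | 24 to 36 (0.80 × 30 = 24; 1.20 × 30 = 36) | 35, 36 kept |

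On the 30-dose schedule, 24 and 25 doses are 80.0% and 83.3% of schedule but score 75.0% and 78.1%. Counts of 37 and 38 are 123.3% and 126.7% of schedule but score 115.6% and 118.75%. On the 29-dose schedule the lower limit misclassifies no whole-dose count.

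**Sensitivity to date recording.** If a site enters the Visit 4/7 date as the stop date but the counter includes the next morning's dose, the score is 30/30 = 100%. The same behaviour can therefore score 93.75% or 100%.

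**Sensitivity to Protocol 8.3.1.** Read literally, its visit-day instruction would remove the morning doses of Day 1 and Day 14. The score then falls to 28/32 = 87.5% or 27/30 = 90%. That instruction and the twice-daily schedule contradict each other and must be reconciled.

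**The case against.** The strongest reply is that 80% and 120% are chosen cut-offs on a score the SAP defines explicitly, and they are applied exactly as written. No stated figure fails to reproduce. That is fair as far as it goes. But item 4 presents the limits as bounds on taking the medication required each day, and a score that cannot reach 100% on the protocol's own schedule does not measure that.

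The second reply concerns the inputs. The morning dose after Visit 4/7 is implied by the order of events in Protocol 8.3.3.4, not spelled out, and the SAP does not say how sites date the end of DISKUS use. This stands. It is why two schedules are shown, and why a reader should not infer that every DISKUS figure is too low: under one plausible way of recording dates the score is exactly 100%. Nor do 85.3% and 128% describe the limits generally; they belong to the 30/32 case only.

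The third reply is materiality, and it also stands. On the schedules above, a fully adherent subject scores at least 93.75%, well clear of 80%. Exclusion is by period. Both treatments include a twice-daily DISKUS, so the scoring rule is the same for each and has no built-in direction.

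**Conclusion.** The denominator is wrong as written for the DISKUS, and nothing in the SAP corrects for the half days. Under the two stated assumptions, full adherence scores 96.7% or 93.75%. The Per Protocol limits act as 82.8% and 124.1%, or 85.3% and 128%, of scheduled doses. The first-day error needs only the evening start; the last-day error also needs the implied morning dose.

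The effect is confined to the DISKUS compliance table and to periods within a dose or two of a limit in the confirmatory Per Protocol analysis. A reader might infer that adherent subjects are dropped or that the trial's main result is affected. The documents do not support either: only subjects who missed five or six of 30 doses are wrongly excluded, and the primary test and the testing hierarchy use the ITT population. This is a minor correction.

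**What to change.** In SAP 10.6.2, make the DISKUS denominator the number of scheduled doses: 2 × (Stop_Date − Start_Date + 1), minus 1 for the evening-only first day, and minus 1 more when Stop_Date is the day after the Visit 4/7 evening dose. On the schedules above this gives 30 − 1 = 29 and 32 − 2 = 30, so full adherence scores 100%.

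State that the stop date is the date of the last DISKUS dose, so that it matches the counter reading. Without this, a Day 14 stop date combined with a counter that includes the Day 15 morning would score 30/29 = 103.4%.

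Keep the 80% and 120% limits and the ELLIPTA formula. Reconcile the visit-day instruction in Protocol 8.3.1 with the twice-daily schedule, and make the scheduled-dose count follow the outcome.

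The cost is a small programming change using dates already held, plus a line of text on the stop date. One limitation remains: for an early withdrawal whose last dose was a morning dose, the last day may still be off by one.

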10.6.3. Efficacy

Primary Endpoint

Maximal % Decrease from Pre-Exercise FEV₁ Following 12 Hour Challenge at Day 14

The primary endpoint will be derived as follows:

$$\frac{\text{Pre-Exercise FEV}_1 - \text{Minimum Post Exercise FEV}_1}{\text{Pre-Exercise FEV}_1} \times 100$$

Where pre-exercise FEV₁ will be defined as the FEV₁ value collected immediately prior to the exercise challenge.

And the minimum post exercise FEV₁ will be the smallest FEV₁ value recorded from the planned post-challenge time points (5, 10, 15, 30, 45 and 60 minutes) using only those with an actual time that is no more than 65 minutes after the challenge stop time.

The minimum post exercise FEV₁ will only be calculated if there are at least the following non-missing FEV₁ values:

- A post-exercise measurement with an actual time of ≤ 17 minutes
- A post-exercise measurement with an actual time of ≥ 25 and ≤ 50 minutes

If there are not values meeting both of these criteria available then the endpoint will not be calculated and will be treated as missing.

Secondary and Other Endpoints

Maximal % Decrease from Pre-Exercise FEV₁ Following Exercise Challenge

Maximal percent decrease from pre-exercise FEV₁ will be derived for other time points in the same way as for the primary endpoint.

Maximal Decrease from Pre-Exercise FEV₁ (L) Following Exercise Challenge

Maximal decrease from pre-exercise FEV₁ (L) will be derived as:

$$\text{Pre-Exercise FEV}_1 - \text{Minimum Post Exercise FEV}_1$$

Where pre-exercise FEV₁ and minimum post-exercise FEV₁ are defined in the same way as for the primary endpoint and the same minimum number of non-missing FEV₁ values are required for the endpoint to be calculated.

Maximal % Decrease from Period Baseline FEV₁ Following Exercise Challenge

Maximal percent decrease from period baseline FEV₁ will be derived as:

$$\frac{\text{Period Baseline FEV}_1 - \text{Minimum Post Exercise FEV}_1}{\text{Period Baseline FEV}_1} \times 100$$

Where minimum post-exercise FEV₁ is defined in the same way as for the primary endpoint and the same minimum number of non-missing FEV₁ values are required for the endpoint to be calculated.

Secondary and Other Endpoints
Maximal Decrease from Period Baseline FEV₁ (L) Following Exercise Challenge
Maximal decrease from period baseline FEV ₁ (L) will be derived as:
Period Baseline FEV₁ – Minimum Post Exercise FEV₁
Where minimum post-exercise FEV ₁ is defined in the same way as for the primary endpoint and the same minimum number of non-missing FEV ₁ values are required for the endpoint to be calculated.
Proportion of Subjects With a Post-Challenge FEV₁ No More Than 5% Lower Than Their Pre-Exercise FEV₁
Subjects meeting the criteria will be those who had a post-challenge FEV ₁ \geq 95% of their pre-exercise FEV ₁ . For the time point in question, each subject's post-challenge FEV ₁ as a percentage of their pre-exercise FEV ₁ will be derived as follows:
$\frac{\text{Post Exercise FEV}_1}{\text{Pre-Exercise FEV}_1} \times 100$
If this number is \geq 95% then the subject will have met the criteria.
% of Subjects with a Decrease from Pre-Exercise FEV₁ in 3 Categories
For the time point in question, each subject's percentage decrease from pre-exercise FEV ₁ will be derived as follows:
$\frac{\text{Pre-Exercise FEV}_1 - \text{Post Exercise FEV}_1}{\text{Pre-Exercise FEV}_1} \times 100$
Subjects will then be allocated to one of the 3 categories.
Weighted Mean 0-60 Minutes for % Decrease from Pre-Exercise FEV₁ Following Exercise Challenge
For each time point, the percentage decrease from pre-exercise FEV ₁ will be derived as follows:
$\frac{\text{Pre-Exercise FEV}_1 - \text{Post Exercise FEV}_1}{\text{Pre-Exercise FEV}_1} \times 100$
The weighted mean will then be calculated as the average area under the curve (AAUC) using the trapezoidal rule, and dividing by the relevant time interval. The 0 minute value, coming from the pre-exercise measurement, will be 0 by definition and actual times will be used for all other measurements in the calculation of the AAUC.
The AAUC will be calculated from the first non-missing time point to the last non-missing time point. If one or more observations are missing between two non-missing observations, the value(s) will be linearly interpolated between the two non-missing values.
The AAUC ($t_0 - t_L$ mins) will be calculated as follows:

Secondary and Other Endpoints

$$\text{AAUC}_{(t_0-t_L \text{ mins})} = \frac{\frac{1}{2} \sum_{i=0}^{L-1} (C_i + C_{i+1})(t_{i+1} - t_i)}{t_L - t_0}$$

Where,

i = collected measurement

L = last collected measurement

C_i = result of collected measurement i

t_i = actual time of assessment for collected measurement i

For the weighted mean over 0-60 minutes, only scheduled planned times (5, 10, 15, 30, 45 and 60 minutes) will be used for the post-exercise time points and only those with an actual time that is less than or equal to 65 minutes after the challenge stop time. The AAUC will only be calculated if there are at least the following non-missing values:

- The 0 hour (pre-exercise) measurement
- A post-exercise measurement with an actual time of ≤ 17 minutes
- A post-exercise measurement with an actual time of ≥ 25 and ≤ 50 minutes
- A post-exercise measurement with an actual time of ≥ 55 and ≤ 65 minutes

If any of these values are missing then the AAUC will not be calculated, and the endpoint will be treated as missing.

ACQ-5

The Asthma Control Questionnaire-5 (ACQ-5) is a five-item questionnaire and there are 7 answers to each question that are associated with the numbers 0-6, where 0 represents no impairment and 6 represents maximum impairment. The ACQ-5 score is the mean of the 5 items and therefore gives a value between 0 (well controlled) and 6 (extremely poorly controlled). The ACQ-5 score will only be calculated if all 5 items of the questionnaire are non-missing.

Physical Activity Measures Assessed by Biosensor

For the physical activity measures assessed by the biosensor, the week 2 time point will be derived using all the available data from the last 7 calendar days prior to, but not including the last scheduled clinic visit of the treatment period (Visit 4/7). For example, if Visit 4 was on the 18th May then the week 2 time point for treatment period 1 would be derived as the average of the non-missing data that is available between the 11th May and the 17th May inclusive.

